Due to the high cost of sugammadex, some researchers have hypothesized that a lower dose is required when combined with neostigmine. A 2015 study from Beirut in adults undergoing elective surgery demonstrated that a dose of 2 mg/kg of sugammadex combined with neostigmine 0.05 mg/kg was non-inferior to the standard dose of 4 mg/kg of sugammadex in reversing deep NMB, defined as returning from a TOF count of 0 to a TOF ratio of 0.9 within 5 minutes, with similar times to extubation as well as no cases of recurarization in the post anesthetic care unit (PACU) (16). Lobaz, Sammut and Damodaran reported in 2013 the use of sugammadex as rescue therapy for a 71-year-old patient with end stage renal disease who was unable to be weaned off the ventilator almost five hours after receiving a single 1.2 mg/kg dose of rocuronium. He had initially achieved a TOF of 4, was reversed with 2.5 mg of neostigmine 45 minutes after induction, but failed to maintain adequate spontaneous ventilation despite his TOF remaining at 4, and was transferred to the intensive care unit 3 hours post induction. There, his TOF steadily declined to 2, as a result of which he received a 6 mg/kg dose of sugammadex, causing him to be successfully extubated ten minutes later (17). It is similarly important to dose sugammadex appropriately; Carollo et al. published a case report in 2019 of an 8-month-old patient who had recurarization after a 4 mg/kg dose of sugammadex was given with a TOF count of 2/4, which fortunately resolved after a second 4 mg/kg dose of sugammadex (18).

Lastly, known common adverse effects of neostigmine include bradycardia, nausea and vomiting (19), while the use of sugammadex has been found to lead to nausea, vomiting, hypotension and headache in \geq 10% of patients (5). There have also been case reports of marked bradycardia possibly leading to cardiac arrest with the use of both agents.

Page 6 of 30 Version: 3 (10/14/2024)

4. Study Endpoints

Primary study outcome:

The time taken to achieve a TOF ratio of 0.9 after the use of the intervention drug versus placebo in a patient population that has already received neostigmine for NMB reversal.

Secondary study outcome:

The percentage of patients who achieve a TOF ratio of 0.9 within 1 minute, 2 minutes, 5 minutes, and 10 minutes.

Safety outcomes:

The incidence in PACU (measured in %) of:

- i. Nausea,
- ii. Vomiting,
- iii. Bradycardia²,
- iv. Tachycardia³, and
- v. Hypotension⁴.

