These patients will be randomized using the Emory University REDCap (Research Electronic Data Capture) software to six groups: 2 mg/kg (the lowest dose approved by the FDA), 1 mg/kg, 0.5 mg/kg, 0.25 mg/kg, 0.125 mg/kg of sugammadex and placebo. Doses would be based on actual body weight. The time taken to reach a TOF ratio of 0.9 thereafter would be measured. If the patient fails to achieve this goal by 10 minutes, sugammadex would be given in 2 mg/kg increments until the patient reaches this threshold and can be safely extubated. The TOF ratio would be measured again at 30 minutes after arrival at the PACU to exclude delayed residual NMB with the plan to give further 2 mg/kg doses of sugammadex if detected.

The inclusion of a placebo group would allow us to examine if patients may recover spontaneously over that time without needing any sugammadex at all, and what parameters may predict that subset of patients. It will also improve the dose response modelling, in that randomization has been weighted so that patients who are least likely to need sugammadex (i.e. if they achieved a TOF count of 4 twitches without fade) are more likely to be in the placebo group or at the lowest dose of sugammadex that is being tested.

The time taken to a TOF ratio of 0.9 after the intervention drug has been given would be compared for statistically significant differences, controlling for the:

- TOF count (3 twitches, 4 twitches with fade, 4 twitches without fade), and
- TOF ratio (0 to < 0.9)

15 minutes after neostigmine has been given and prior to giving the intervention drug.

Quantitative neuromuscular monitoring will be carried out using electromyography, which measures the TOF ratio every 20 seconds. The TOF count (between 0 to 4) and the TOF ratio (0 to 1) would be measured and recorded at baseline and after administration of the study drug. If the TOF ratio remains < 0.9 after this, or if the patient exhibits any symptoms or signs of residual NMB blockade, a further 2 mg/kg dose of sugammadex would be given until the patient achieves a TOF ratio of 0.9.

Page 8 of 30 Version: 3 (10/14/2024)

7. Statistical Analysis Plan

Power Analysis

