An *a priori* power analysis was conducted using G*Power 3.1.9.4 (20). We used an ANOVA F-Test for one-way omnibus difference between groups, alpha threshold of 0.05 for rejecting the null hypothesis, statistical power of 0.80 and a "very large" effect size of 0.765 was calculated based on results from a 2013 randomized controlled trial that examined time from TOF count = 4 to TOF ratio 1.0 comparing neostigmine to three different doses of sugammadex: 0.5, 1.0, and 2.0 mg/kg (15). This gave a required sample size of N=24. This number was increased to N=36 to account for patients with poor modeling from a high starting TOFR (resulting in few data points for that patient) or incomplete recovery within the maximum ten minutes allotted. An anticipated 70% of those enrolled will become ineligible because of an initial TOFR of 90% or greater, thus not requiring any medications, so up to 120 patients may need to be recruited and screened, but only 36 will receive any treatment.

Methodology

Randomization will occur with permuted block randomization, divided into 18 groups, to ensure proportional allocation of participants in each group over time. Dose randomization will be assigned after stratifying by initial TOFC, with a set number of patients recruited for each group, as seen the table below. This ensures that patients who likely need a lower dose are more likely to receive it. Randomization will not occur until participation is assured, i.e., their TOFR is <0.90.

Table 1: Randomization plan for patients (n=36)

| Sugammadex Dose (mg/kg) → | | 0.00 | 0.125 | 0.25 | 0.50 | 1.00 | 2.00 | | | |
|---------------------------|-----------------|------|--|----------|------------|---------|---------|------|-------|----|
| Initial TOFR | Initial TOFC | Fade | placebo | | | | | | Total | |
| ≥ 0.9 | NA | NA | No treatment; track for adverse events | | | 0 | | | | |
| | | 4 | No | 3 pt | 3 pt | 2 pt | 2 pt | 1 pt | 1 pt | 12 |
| < 0.9 | 4 | Yes | 2 pt | 2 pt | 2 pt | 2 pt | 2 pt | 2 pt | 12 | |
| | 3 | NA | 1 pt | 1 pt | 2 pt | 2 pt | 3 pt | 3 pt | 12 | |
| < 0.9 | 0-2 | NA | No t | treatmen | t; track f | or adve | se even | ts | 0 | |
| Total # of Patients (pt) | | | 6 | 6 | 6 | 6 | 6 | 6 | 36 | |

Statistical Methodology

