Assuming assumptions are valid, an increasing exponential regression model with random intercept will be fitted with Time of Four Ratio versus Time, stratified by the natural log of the five dose levels (modeled below). This translates to a slow response initially followed by a more rapid response later. The random intercept will allow for different initial TOFR values.

Page 9 of 30 Version: 3 (10/14/2024)

$$TOFR = \frac{1}{B}e^{(A+time)/B} + TOFR_{initial} + C * \ln(dose)$$

"Success" will be defined as TOFR of ≥0.9 within 5 minutes for 95% of patients, following the model estimate, adjusting for the 95% confidence intervals of the estimates, based on initial TOF ratios, which may be grouped as needed. A secondary analysis will be conducted by TOFC to determine optimal dose at each TOFC level, and if TOFC correlates strongly with TOFR.

8. Data and/or Specimen Banking

N/A

9. Sharing of Results with Participants

N/A

10. Study Timelines

All subjects are anticipated to participate in the study from the start of their surgery to the time of their discharge from the PACU, which should be on the same day. It is expected that 1 year would be required to enroll all study subjects, and for the study to be completed by July 2023.

11. Inclusion and Exclusion Criteria

Individuals will be screened for eligibility at the anesthesia pre-admission clinic.

Inclusion criteria:

- Patients aged 18 years and above who will
- Undergo an elective surgery in the main operating room or outpatient surgery center at Grady Memorial Hospital,
- Receive general anesthesia (standardized to sevoflurane for maintenance),
- Receive rocuronium for NMB,
- Receive neostigmine for NMB reversal,
- Achieve a TOF count of at least 3 twitches but not a TOF ratio of 0.9 fifteen minutes after neostigmine has been given, and
- Able and willing to provide informed consent.

Exclusion criteria:

Page 10 of 30 Version: 3 (10/14/2024)

- Pregnancy and/or lactating,
- BMI ≥ 40,
- Severe renal impairment, i.e. chronic kidney disease stages IV and V as defined by GFR < 30 ml/min/1.73 m² (21),
- Severe hepatic impairment, i.e. Child-Pugh score C⁵ (22, 23),
- Pre-existing neuromuscular disease,
- Anticipated need for postoperative intubation, and/or
- Known hypersensitivity reactions to rocuronium, neostigmine and/or sugammadex.

12. Population

We will not be including the following special populations:

- Adults unable to consent
- Individuals under the age of 18 years
- Pregnant women

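### Section 7's Success model omits the TOFC randomisation stratum and cannot take the placebo arm; the Section 6 comparison of times has no named method, and time after rescue is undefined

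*Combined protocol and SAP*

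**What the plan says.** - **Section 4** gives the primary outcome: "The time taken to achieve a TOF ratio of 0.9 after the use of the intervention drug versus placebo".
- **Section 6** says these times "would be compared for statistically significant differences, controlling for the" TOF count and TOF ratio measured before study drug. The first covariate is listed as "TOF count (3 twitches, 4 twitches with fade, 4 twitches without fade), and" the second is the ratio itself. No test or model is named. Of the placebo group the section says: "It will also improve the dose response modelling", and it ties this to the weighted randomisation.
- **Section 7, Power Analysis**: "We used an ANOVA F-Test for one-way omnibus difference between groups". The ANOVA appears nowhere else.
- **Section 7, Methodology**: "Dose randomization will be assigned after stratifying by initial TOFC, with a set number of patients recruited for each group". Table 1 gives the counts.
- **Section 7, Statistical Methodology** has one equation, for TOFR against time, "stratified by the natural log of the five dose levels (modeled below". Its terms are time, initial TOFR and C·ln(dose). Success (TOFR at least 0.9 within 5 minutes for 95% of patients) is read from this model, "based on initial TOF ratios, which may be grouped as needed". TOFC enters only through a secondary analysis by TOFC level, with no model stated.
- **Rescue**: under Section 6, patients below 0.9 at 10 minutes receive further sugammadex. In Section 7, incomplete recovery appears only as a reason to raise N from 24 to 36. Section 20 lists time to TOFR 0.9 in seconds, with no time or indicator of rescue.

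**The concern.** Allocation to dose differs by TOFC, so TOFC is a randomisation stratum with unequal ratios. The deeper-block stratum is over-represented at the higher doses, and an analysis that ignored it would understate the effect of dose. Section 6 recognises this. Section 7 neither carries the adjusted comparison forward nor puts TOFC in the model that selects a dose.

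The drug-versus-placebo part of the primary outcome has covariates but no named method. The dose-response model leaves out the arm that Section 6 says will help it. The primary time is undefined for anyone rescued at 10 minutes, and those patients are likely to cluster at placebo and the low doses. Each gap leaves a choice that could be made after the data are seen.

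**Working it through.** **1. The plan's own figure.** Inputs from Section 7: f = 0.765, alpha 0.05, power 0.80. The noncentrality is f²N = 0.585 × 24 = 14.05. With four groups (3 and 20 df) power is 0.824, so N = 24 reproduces with the four groups of the cited trial. With this trial's six groups, N = 24 gives 0.700 and N = 36 gives 0.920. (The group count is a separate matter.) The calculation has no covariates. Adding TOFC (2 df) and initial TOFR (1 df) at N = 36 leaves 27 error df and power 0.914, counting only the loss of df.

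**2. How far dose depends on TOFC (Table 1).**

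| Stratum | 0 | 0.125 | 0.25 | 0.5 | 1 | 2 mg/kg | Mean dose score (0–5) |
|---|---|---|---|---|---|---|---|
| 4 twitches, no fade | 3 | 3 | 2 | 2 | 1 | 1 | 22/12 = 1.83 |
| 4 twitches, fade | 2 | 2 | 2 | 2 | 2 | 2 | 30/12 = 2.50 |
| 3 twitches | 1 | 1 | 2 | 2 | 3 | 3 | 38/12 = 3.17 |

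- Total sum of squares of the score: 6 × 17.5 = 105.
- Between strata: 2 × 12 × 0.667² = 10.67. Left after TOFC: 94.33.
- Correlation with block depth (scored 0, 1, 2): 16/√(105 × 24) = 0.319.
- Variance inflation from adding TOFC: 105/94.33 = 1.113, so the SE rises by a factor √1.113 = 1.055.

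If each TOFC step added an assumed 1, 2 or 3 minutes, a crude comparison of 2 mg/kg with placebo would be off by 0.67, 1.33 or 2.0 minutes, against the higher dose.

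**3. Confounding left once initial TOFR is in the model.** This is an illustrative log-normal time model with a true slope of −0.30 per dose step and all effects assumed. Its TOFR ranges follow the documents: 0.10–0.40 with fade (Section 3); 0 with three twitches, since TOFR is T4/T1 and T4 is absent; 0.40–0.89 without fade. Over 15 scenarios:
- Initial TOFR only: −0.286 to −0.301. Largest bias 0.014/0.300 = 4.7%, about a quarter of the n = 36 sampling SD of 0.055.
- TOFC plus initial TOFR: −0.297 to −0.303.

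A separate linear model (true slope −1.5 minutes per ln dose) let TOFR track TOFC only loosely. TOFR alone then gave −1.41 to −1.22, a bias of 6% to 19%. That needs three-twitch patients with TOFR clearly above zero, which the T4/T1 definition does not allow.

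**4. What placebo adds to the slope.** The active doses double at each step, so the score is ln(dose) rescaled. The 30 active patients split 9/10/11 by stratum, with mean scores 22/9, 3 and 38/11.
- Without placebo: 60 − (9 × 0.556² + 11 × 0.455²) = 60 − 5.05 = 54.95.
- Placebo kept, with its own indicator: 55.69, a gain of 1.3%.
- Placebo scored one step below 0.125 mg/kg, as if it were 0.0625 mg/kg: 94.33. The ratio to 54.95 is 1.72, and √1.72 = 1.31 on the SE.

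**5. Time after rescue.** Assume log-normal times with log-SD σ = 0.6 and median m, and let z = ln(10/m)/σ. The mean without rescue is M = m·exp(σ²/2). Capped: M·Φ(z−σ) + 10(1−Φ(z)). Through rescue: the same with 11.8 for 10, adding the 1.8-minute average that Section 3 cites for 2.0 mg/kg. Dropped: M·Φ(z−σ)/Φ(z).

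| Median | Past 10 min | No rescue | Capped | Through rescue | Dropped |
|---|---|---|---|---|---|
| 5 | 12% | 5.99 | 5.49 | 5.72 | 4.86 |
| 12 | 62% | 14.37 | 8.82 | 9.94 | 6.91 |
| Difference | | 8.38 | 3.33 | 4.22 | 2.05 |

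All three shrink the contrast between a slow and a fast group. In the 15 scenarios of step 3, fully adjusted, censoring recovers −0.30. Capping gives −0.20 to −0.29, time through rescue −0.23 to −0.30, and dropping −0.20 to −0.28.

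**The case against.** The two sections do not compete. Section 6 compares times and Section 7 models TOFR over time, so a reader who infers two rival covariate sets for one analysis goes beyond the text. In a combined document, Section 6 already fixes the outcome, the comparison and both covariates. This stands: what is missing is the method, and its statement in the analysis plan.

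Initial TOFR is in the Section 7 model and takes up most of what TOFC carries. This also stands, and it makes the TOFC omission small in numerical terms.

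The model's five dose levels may be a deliberate active-dose model. Placebo's first stated purpose is to study spontaneous recovery, and the modelling gain is tied to weighted allocation. That is a fair reading, but then no passage says how placebo enters any dose-response analysis. It is tempting to say that leaving placebo out inflates the SE by 31%. The documents do not support this, because the figure rests almost wholly on placing placebo one step below 0.125 mg/kg.

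A reader might also infer that the silence on rescue favours the low-dose hypothesis. Success is read from a TOFR curve at 5 minutes, and a patient not recovered at 10 minutes contributes readings below 0.9 without any imputed time. The percentages recovered by 1 to 10 minutes are unaffected. The strongest flattening from capping came where the assumed 0.5 mg/kg median was 6.1 to 6.6 minutes, against the 4.1-minute average to TOFR 1.0 cited in Section 3. With medians of about 3.7 to 4.1 minutes, capping gave −0.26 to −0.275. The objection stands for Success, but the rule for the primary time is still missing.

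**Conclusion.** The point holds as a gap in specification. Four things follow from the text alone: the Section 6 comparison has no named method; the Success model lacks the stratum that sets the allocation ratios; 6 of 36 patients (17%) cannot enter that model as written; and the primary time is undefined after rescue.

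The numerical consequences are more limited. Residual confounding after initial TOFR is likely 5% or less under the documents' TOFR ranges, with assumed recovery effects. The precision gain from placebo runs from almost nothing to substantial, depending on coding. The flattening from rescue handling concerns the time outcome only, and its size depends on assumed recovery times. It is not shown to alter Success.

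No passage plans an unadjusted comparison of times, and none says that patients who do not recover will be excluded. Neither should be read into the plan. This should be fixed before the data are analysed.

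**What to change.** In Section 7:

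1. Name the Section 6 comparison of time to TOFR 0.9, across all six groups, as the primary analysis. Adjust for the three-level TOFC stratum and initial TOFR. Keep all 36 randomised patients and right-censor time at first rescue or 10 minutes, whichever is earlier. Pre-specify one censored-time model, for example log-normal accelerated failure time or Cox.
2. Add the TOFC stratum to the TOFR-time model. Replace ln(dose) with a pre-specified term defined at zero, for example a placebo indicator plus ln(dose) among active doses. Exclude TOFR readings taken after rescue.

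The cost is wording, one standard model and two degrees of freedom for TOFC. From Table 1 the SE of the dose slope is about 5.5% larger than with no covariate, and adding TOFC to initial TOFR left the simulated SD at 0.055–0.056. The data list in Section 20 would also need the time of first rescue. A placebo indicator avoids assuming where placebo lies on the dose scale but adds little precision to the slope. No dose or rescue rule changes.

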A Cochrane systematic review published in 2017 (12) analyzed 41 randomized controlled trials of 4,206 adults who received non-depolarizing NMBAs for elective surgery, and found that a 2 mg/kg dose of sugammadex was 6.6 times faster (10.22 minutes) than a 0.05 mg/kg dose of neostigmine in reversing moderate NMB from the second twitch (T2) to a TOF ratio > 0.9, while

_

¹ The ratio of the fourth (T4) to the first (T1) twitch after a TOF stimulation

a 4 mg/kg dose of sugammadex was 16.8 times faster (45.78 minutes) than a 0.07 mg/kg dose of neostigmine in reversing deep NMB from a PTC 1-5 to TOF ratio > 0.9.

However, less is known when there is shallow NMB, i.e. when the TOF count is 4 but there is still detectable TOF fade. Concerningly, Kirkegaard *et al.* found in 2002 that the maximal 0.07 mg/kg dose of neostigmine was unable to reverse all patients to a TOF ratio of 0.9 within 30 minutes, even at a pre-intervention TOF count of 4 (13). Whether a lower dose of sugammadex would be sufficient to achieve a TOF ratio of 0.9 after shallow NMB has been examined by Schaller *et al.* in 2010 and Pongrácz *et al.* in 2013. The former group found that in a group of 94 adults undergoing elective surgery, a dose of 0.22 mg/kg of sugammadex was equivalent to a dose of 0.034 mg/kg of neostigmine in reversing NMB from a TOF ratio of 0.5 to 0.9 within 5 minutes in 95% of their patients (14). Conversely, Pongrácz's group found that a 0.5 mg/kg dose of sugammadex reversed NMB from a TOF count of 4 to a TOF ratio of 1.0 in 4.1 minutes on average compared to 2.1 minutes for a 1.0 mg/kg dose of sugammadex, 1.8 minutes for a 2.0 mg/kg of sugammadex, and 8.5 minutes for a 0.05 mg/kg dose of neostigmine (15).

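### The planned recovery curve accelerates without limit although the TOF ratio cannot exceed 1, and the 5-minute success rule is read from that curve

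*Combined protocol and SAP*

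**What the plan says.** Section 7, Statistical Methodology, states that "an increasing exponential regression model with random intercept will be fitted with Time of Four Ratio versus Time". Its formula is TOFR = (1/B)·exp((A + time)/B) + TOFR_initial + C·ln(dose). The shape is described in words: "This translates to a slow response initially followed by a more rapid response later". The random intercept is there to accommodate different starting TOF ratios. The same section defines success as 95% of patients at a TOF ratio of at least 0.9 by 5 minutes, judged from the model estimate and its confidence limits. The model is made conditional on its assumptions holding, but no check and no alternative model are named.

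Section 6 (Procedures Involved) fixes the range and timing of the response: "the TOF ratio (0 to 1) would be measured and recorded at baseline and after administration of the study drug", with a monitor "which measures the TOF ratio every 20 seconds". The Power Analysis in section 7 refers to "incomplete recovery within the maximum ten minutes allotted". It also notes that a high starting ratio leaves a patient with few data points, which hints that a series ends near 0.9. No passage states the fitting window. The data list in section 20 contains the time to 0.9 and the ratio 30 minutes after PACU arrival, but no serial ratios after the study drug.

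The Background gives average times to a TOF ratio of 1.0, without prior neostigmine, of 4.1 minutes at 0.5 mg/kg, then "2.1 minutes for a 1.0 mg/kg dose of sugammadex, 1.8 minutes for a 2.0 mg/kg of sugammadex".

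**The concern.** A response that starts below 0.9, rises and cannot pass 1 must slow down as it nears its limit. The planned curve does the opposite: it speeds up indefinitely. This is a matter of shape over time, and it remains even with one dose and one starting value.

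The trial's objective is to find an appropriate dose, and success is judged on the fitted curve. If the shape is wrong, the fitted time to 0.9 depends on how many flat readings after recovery are included. A dose's verdict could then turn on an unstated data-handling choice rather than on the drug.

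**Working it through.** The plan states no figure for the accuracy of the curve, so there is none to reproduce. Its N=24 comes from a one-way ANOVA and does not involve the curve.

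**Shape when B > 0.** The second derivative in time is (1/B³)·exp((A + time)/B). It is positive everywhere, so the curve is convex and has no upper limit. The verbal description requires this case.

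**Shape when B < 0.** The time term is negative and rises to zero, so the curve levels off at TOFR_initial + C·ln(dose). At 1 mg/kg, ln(1) = 0 and the ceiling is TOFR_initial. If that is the observed start, it is below 0.9 for every eligible patient.

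**Assumed truths (not in the documents).** The starting ratio y0 is 0.2, 0.4 or 0.6, the true time to 0.9 is T, and readings come every 20 seconds (section 6). Two bounded curves were used, giving six scenarios for each T:

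- Saturating: 1 − (1 − y0)·exp(−kt), with k = ln((1 − y0)/0.1)/T.
- Sigmoid: y0 + (1 − y0)·t³/(t³ + m³), with m set so that the ratio is 0.9 at T.

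Example (saturating, y0 = 0.4, T = 4): k = ln(6)/4 = 0.448. The ratio is 1 − 0.6·exp(−0.896) = 0.755 at 2 minutes, 0.900 at 4 and 1 − 0.6·exp(−4.48) = 0.993 at 10. The rise is 0.355 in the first two minutes, 0.145 in the next two and 0.093 in the last six.

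**Single-curve fits.** The planned form (B > 0, free intercept) was fitted by least squares without noise. The error is fitted minus true time to 0.9, for T from 2 to 5 minutes:

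| Readings fitted | Error (min) |
|---|---|
| Up to 0.9 | −0.7 to −0.05 |
| Up to 1 min after 0.9 | −0.2 to +0.3 |
| Up to 2 min after 0.9 | +0.2 to +0.8 |
| All 10 min | +1.1 to +3.2 |

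With all 10 minutes, B runs to the limit of its search range, so the best increasing exponential is a straight line. A true 4 minutes is then fitted at 5.5 to 6.4 in all six scenarios (5.82 in the example above). At T = 7 the error falls to +0.3 to +0.6.

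**Can an adequate dose fail?** Assume a median of 3.3 minutes and a log-scale SD of 0.2 between patients. The 95th percentile is 3.3·exp(1.645 × 0.2) = 4.6 minutes, so the dose meets the rule. Fitted to 10 minutes, the curve crosses 0.9 at 5.4 to 5.9 minutes. A noise-free single-curve repeat over the six scenarios gives 4.9 to 6.0, above 5 in five of them; the exception is saturating recovery from 0.6. A typical curve that crosses after 5 minutes cannot show 95% of patients there by 5.

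**Fit at time 0 and at 5 minutes.** In a simulation of 12 patients starting at 0.10 (reading SD 0.02), the fitted value at time 0 was 0.61 to 0.78 with all 10 minutes and 0.45 to 0.56 when stopped at 0.9. In noise-free fits stopped at 0.9, with starts of 0.1 and 0.4 and true times of 2.1 and 4.1 minutes, the 5-minute prediction was 1.07 to 2.35. It falls below 1 only when the true time is itself close to 5 minutes.

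**Pooled fit, one B for all doses.** Assumed true times are 8, 6, 4.1, 2.1 and 1.8 minutes for the five doses in ascending order. Fitted times are shown for y0 = 0.4, with the range over the two truths:

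| True | Free intercepts, to 0.9 | Free intercepts, 10 min | Observed start + C·ln(dose), to 0.9 |
|---|---|---|---|
| 8 | 6.5–6.9 | 8.3–8.8 | 6.6–6.8 |
| 4.1 | 4.5–5.0 | 6.0–6.4 | 5.3–5.7 |
| 2.1 | 3.7–4.0 | 4.5–4.9 | 4.7–5.1 |
| 1.8 | 3.6–3.9 | 4.3–4.7 | 3.9–4.3 |

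Stopped at 0.9 with free intercepts, a true spread of 8 − 1.8 = 6.2 minutes shrinks to about 2.9 to 3.0 (6.45 − 3.60 and 6.92 − 3.93).

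**The case against.** Much of the case on the other side stands, and it limits the point.

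- **Fitting window.** The remark about few data points suggests that series stop near 0.9, and a single curve is then nearly right. A reader might infer that the plan overstates time to 0.9 by a fixed two minutes or so. The documents do not support that. The figure needs all 10 minutes fitted and an assumed true curve; one or two extra minutes give only −0.2 to +0.8, and stopping at 0.9 reverses the sign.
- **Negative B.** A reader might infer that no value of B can describe recovery. That holds only if the intercept is the observed start. With a free intercept and B < 0, saturating data were recovered well (2.1 to 2.4 for a true 2.1; 4.1 to 4.3 for a true 4.1). But the intercept then stands for the plateau, which contradicts both its stated role and the stated shape.
- **The 4.1-minute case is not a false fail.** A median of 4.1 minutes puts 84% of patients at 0.9 by 5 minutes with log SD 0.2, or 65% with 0.5. The 95th percentiles are 5.7 and 9.3 minutes. That dose truly misses the rule, which is why the 3.3-minute case is used above.
- **Inputs.** The published 2.1 and 4.1 minutes are average times to 1.0 without prior neostigmine. Here they serve only as plausible values for time to 0.9.
- **A simple saturating curve is not safe either.** Fitted over 10 minutes to sigmoid data, it gave 5.0 to 5.8 for a true 4.1.
- **Primary outcome.** The observed time to 0.9 can be compared between groups without the curve. This is correct, but the success rule does not use it.

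**Conclusion.** The curve is wrong as written: convex and unbounded for a response bounded at 1, with the dose decision resting on it and no fallback named. That conclusion needs no simulation.

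The size and direction of the error are not in the documents and depend on the unstated fitting window. Under the assumed bounded curves:

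- With all 10 minutes fitted, the error is about +1 to +3 minutes for true times of 2 to 5 minutes, enough to fail a dose that meets the 95%-by-5-minutes rule.
- With fitting stopped at 0.9, single-curve crossings are roughly right or up to 0.7 minutes early, but 5-minute predictions are mostly above 1.
- Pooling doses with one B and stopping at 0.9 compresses the dose-response.

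The planned group comparison of observed times is unaffected.

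**What to change.** Replace the increasing exponential with a bounded rising curve flexible enough for a sigmoid (logistic, Gompertz or Hill, upper limit near 1). Tie its start to the observed pre-dose TOF ratio and let its rate depend on dose. State that readings up to 10 minutes or rescue, whichever is first, are fitted. Check fitted against observed values at time 0 and at the 0.9 crossing. Add the serial 20-second post-drug readings to the data list in section 20.

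Alternatively, base the success rule on a time-to-event analysis of the observed time to 0.9, censored at 10 minutes. That variable is already collected and needs no assumed curve.

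The cost is SAP wording and code, one or two extra parameters in a trial of 36, and some added data capture from a monitor already in use.
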